6.2. Anticipated Adverse Device Effects

List of potential risks and discomforts:

- Tingling or warmth of the skin during the Imago scan (0.4% or a 1 in 269 chance) that resolve at completion of the scan
- Exposure to the laser of the Imago (to both skin and eyes)
- Exposure to the acoustic output
- Phototoxicity when applying fragrance or lotion to the skin prior to scanning

.

6.3. Risk/Benefit Rationale

Seno Medical Instruments, Inc. believes that any potential risk presented by this investigation has been minimized and that adequate testing, safeguards, and safety monitoring have been incorporated into the investigation to further minimize and mitigate the risks.

The laser energy will be set to a level that is known as being below known harmful levels, which is unlikely to harm the thyroid or give any discomfort.

Also, everyone in the examination room will be wearing protective eyewear in order to minimize risk of damage by laser light to the eyes

Seno Medical Instruments, Inc. firmly believes that the value of the knowledge to be gained by conducting this clinical investigation to demonstrate the clinical value of the Imago™ Thyroid Imaging System outweighs the potential risks posed to participating subjects.

7. STUDY PROCEDURES

7.1. Study Procedure Overview

The study procedures and the sequence in which they will occur are defined below in Table 1 below and described in greater detail in Section 7.2:

Table 1: SCHEDULE OF EVENTS

Evaluation	Screening/ Enrollment/Imaging Visit ¹	1 st Biopsy Visit (<45 days after Imaging Visit)	2 nd Biopsy Visit (<45 days after 1 st Biopsy Visit; as applicable)	Additional surgical procedure (<45 days after 2 nd biopsy as applicable)
Informed Consent	X			
Medical History	X			
I/E Criteria	X			
TI-RADS Score	X			
CDU thyroid images (Doppler as applicable) ²	X			
Other images/studies PET, CT, MRI, PET/CT, and Carotid Doppler ² .	X			
Biopsy Decision	X			
Directed Thyroid History	X			
Imago OA Evaluation of thyroid and lymph nodes (as applicable)	X			
Ultrasound Guided FNA and/or core biopsy images of thyroid and lymph nodes (as applicable)		X	X	
Images uploaded to Imaging Core Lab	X			
Adverse Event Evaluation	X			
FNA or Core Biopsy Procedure (s)		X	X	
Surgical Biopsy/Treatment (as applicable)		X	X	X
Histopathology/Cytology Samples Collected including biomarkers (as applicable)		X	X	X
End of Study		X ³	X ³	X ^{4,5}

¹The Screening/Enrollment/ Imaging, and Biopsy Visits may take place on the same date as the discretion of the investigator.

²CDU with or without Doppler (as available - CT, MRI, PET/CT, and carotid ultrasound, strain elastography and shear-wave elastography) within 365 days of baseline Imago Scan

³For benign thyroid nodules, where cytopathology or histopathology is concordant with imaging findings, FNAB or core needle biopsy is the final procedure and End of Study.

⁴If biopsy reveals malignant cytology or histology, further surgical treatment will likely be the final procedure and End of Study. Data associated with additional surgical procedures will only be collected up until the time that the confirmatory biopsy/surgical procedure takes place.

⁵If a central lymph node dissection and/or lateral cervical lymph node dissection was performed during or after the thyroid procedure, surgical and histology data associated with those lymph node procedures will be collected.

7.2. Study Visits and Procedures

7.2.1. Screening/Enrollment/Imaging Visit- Day 1

The following procedures will be conducted at the Screening/Enrollment Visit:

- Perform informed consent;
- Review inclusion /exclusion criteria;
- verify from images and/or reports that a suspicious nodule was seen;
- Confirm that CDU has been performed, for which the site radiologist has recommended either ultrasound-guided FNA and/or US-guided core needle biopsy, and will fall within 365 days of Imago OA procedure.
- Record demographics and directed thyroid history; and,
- TI-RADS CDU-based classification
- Imago Imaging

Upon enrollment, subjects receive a subject number that will be used on all documentation for the subject throughout the study. Subject numbers should be assigned in ascending order, and numbers should not be omitted or reused. The subject number is coupled with the site identification number for unique identification of each subject.

Subjects will undergo the Imago OA procedure. Subjects may be asked to return to the clinic to repeat the Imago scan if (a) the image quality is not acceptable for review by A. [name]. Seno's Medical Director and/or the ICLs quality assurance reviewers (QARs) and (b) they have not yet undergone a biopsy procedure. Any adverse device effects or unanticipated adverse device effects that occur during this visit will be reported to appropriate authorities such as the IRB and FDA. In order to provide technical support, representatives from Seno Medical Instruments, Inc. or their designees may be present during the procedure.

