7.2.2. Biopsy Procedure

Patients will be scheduled for initial biopsy within 45 days of the Imago OA/US procedure. Images of FNAB or Core Biopsy needle within the lesion are collected. If an FNAB is performed and results in insufficient cellularity for cytologic diagnosis and a repeat FNAB or core biopsy is required, this should be scheduled within 45 days after the first biopsy. The investigator is to ensure that the applicable site histopathology/cytology report is obtained. If a surgical procedure is applicable, it would be scheduled within 45 days after the second biopsy. Surgical and histology data will be collected.

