7.5. Enrollment Failures

Subjects deemed enrollment failures according to the quality assurance review or failure to complete the biopsy evaluations) will be replaced during the active enrollment period of the study. The following subjects will be considered enrollment failures and will be followed until all AEs are resolved:

- Subjects found to be ineligible after the scan is conducted;
- Subjects for whom the study device scans do not pass review (Seno Medical Director and/or Imaging Core Lab QAR review); and,
- Subjects who have incomplete or unusable biopsy results.

8. ADVERSE EVENTS, ADVERSE DEVICE EFFECTS, UNANTICIPATED ADVERSE DEVICE EFFECTS AND DEVICE DEFICIENCIES

For the purposes of this study, only Imago device-related adverse events (AE), unanticipated adverse device effects, procedure-related AEs and device deficiencies will be collected. AE and device deficiency collection will commence once the subject has provided written informed consent and the patient has entered OA Imago scanning room.

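### Adverse events are scheduled for evaluation only at the imaging visit, though their collection has no stated end, so later non-serious events in evaluable subjects are likely under-ascertained

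*Combined protocol and SAP*

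**What the plan says.** - **Schedule.** In Table 1 (Section 7.1) the row "Adverse Event Evaluation" has one mark, under the Screening/Enrollment/Imaging Visit. The columns for first biopsy, second biopsy and additional surgery have none.
- **Imaging visit.** Section 7.2.1 says that device effects "that occur during this visit will be reported to appropriate authorities such as the IRB and FDA". It also lets a subject come back for another Imagio scan if image quality fails review and no biopsy has yet been done.
- **Biopsy stage.** Section 7.2.2 asks for needle images and the pathology report, and for surgical cases adds "Surgical and histology data will be collected". It lists no AE assessment.
- **Scope.** The opening of Section 8 states that "only Imago device-related adverse events (AE), unanticipated adverse device effects, procedure-related AEs and device deficiencies will be collected". Collection starts after consent, when the patient enters the scanning room. Section 8.4.1 repeats this. Neither gives an end.
- **Follow-up.** Section 7.5 gives a rule for one group: "The following subjects will be considered enrollment failures and will be followed until all AEs are resolved". Nothing equivalent is written for subjects who remain evaluable.
- **Listed risks.** Section 6.2 includes laser exposure to skin and eyes and "Phototoxicity when applying fragrance or lotion to the skin prior to scanning". It gives no time to onset.
- **Serious device effects.** Section 8.4.2 requires a report to the sponsor within 24 hours of the site becoming aware, whatever the visit.

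**The concern.** Sites collect what the schedule and the visit sections tell them to collect. Here those parts stop asking about AEs after the imaging visit, while Section 8 leaves collection open. A non-serious event after that visit reaches the database only if the subject volunteers it and the site records it.

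Two features add weight:

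- A repeat scan is a second laser exposure on a return visit that Table 1 does not show.
- The one follow-up rule covers enrollment failures. They lie outside the intention-to-diagnose population that Section 12.2 uses for all analyses. The subjects who are analysed have no such rule.

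What is at stake is how a clean safety result would be read. Section 1.4 reports thyroid scans in only 13 subjects so far, with 3 mild AEs, so this study will supply most of the sponsor's thyroid safety experience. Section 6.3 relies on safety monitoring being adequate. A report of no later reactions would carry little weight if no visit was scheduled to ask about them.

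**Working it through.** **1. The time span.** Section 3.2 allows up to 45 days from imaging to first biopsy, 45 more to a second biopsy or surgery, and 45 more to final surgery: 45 + 45 + 45 = 135 days. This reproduces the stated maximum. The one scheduled AE evaluation is on Day 1. A subject at the maximum has none on (135 − 1)/135 = 99% of days; one whose biopsy falls on day 45 has none on (45 − 1)/45 = 98%. These are upper ends: the stated minimum participation is 48 hours, and Table 1 lets imaging and biopsy share a date.

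**2. The one device-event rate given.** Section 6.2 puts tingling or warmth at 1 in 269. 1/269 = 0.37%, which agrees with the stated 0.4%. It describes sensations that end with the scan, so it says nothing about later events.

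**3. What a zero count would mean.** With no events in n subjects, the exact one-sided 95% upper bound is 1 − 0.05^(1/n).

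- n = 100 (evaluable target): 1 − 0.05^(1/100) = 2.95%.
- n = 110 (enrolled, Section 4.1): 1 − 0.05^(1/110) = 2.69%.

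The second is the more natural safety denominator, because enrollment failures may also have been scanned. Under the present schedule either bound has systematic enquiry behind it for events at the imaging visit only.

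**4. Illustration of under-ascertainment.** The documents give no rate for later events. Assume a true rate p per subject and a fraction a of events that is captured, with 110 subjects. The expected count seen is 110·p·a, and P(at least one seen) = 1 − (1 − p·a)^110.

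| Assumed p | a = 1 | a = 0.5 | a = 0.25 |
|---|---|---|---|
| 1% | 1.1 seen; P = 0.67 | 0.55; 0.42 | 0.28; 0.24 |
| 2% | 2.2; 0.89 | 1.1; 0.67 | 0.55; 0.42 |
| 5% | 5.5; 0.996 | 2.75; 0.94 | 1.38; 0.75 |

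At an assumed 2%, the chance of seeing even one such event falls from 0.89 to 0.42 if only a quarter are captured. Both p and a are assumptions.

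**5. What counts as procedure-related.** The term is not defined. Sections 7.2.1 and 7.2.2 call the Imagio scan a procedure; Table 1 and Section 7.2.2 use the same word for biopsy and surgery. Section 8.1.1 includes events related to the procedures involved without naming them. Two readings follow:

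- *Scan only.* Table 1 places its AE evaluation where the scan takes place. The gap is then later scan effects and repeat scans.
- *Biopsy included.* Every visit at which a biopsy or surgery takes place lacks an AE evaluation. Section 1.4 records a post-biopsy hematoma as an AE in the sponsor's Dutch breast study, not related to the device. No scheduled question here would bring out such an event.

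The gap exists on both readings; its extent differs.

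**The case against.** The strongest reply is that absence of a scheduled check is not absence of collection.

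- Sections 8 and 8.4.1 open AE collection and never close it. Section 8.4.2 runs from awareness, Section 8.4.3 has no visit limit, and Section 13.9.2 makes failure to report serious or unanticipated device effects within 24 hours of discovery a ground for terminating a site. **This stands.** A reader might infer that later events are systematically missed; the documents do not support that, least of all for serious device effects. But a duty that begins on learning of an event prompts nobody to ask, and Section 8.4.2 covers serious device effects only.
- The visit-limited sentence in Section 7.2.1 sits in the description of that visit and concerns reporting to authorities. **This stands**: it does not by itself restrict Section 8.
- A reader might infer a flat contradiction between Table 1 and Section 8. That needs procedure to mean biopsy, which is not established. **This stands**: what can be shown is a mismatch and an undefined term.
- Delayed phototoxicity is an assumption. Section 6.2 ties phototoxicity to fragrance or lotion applied beforehand, and Section 4.2 excludes photosensitive subjects. **This stands**, but the point does not depend on delayed skin effects: the single mark, the unscheduled repeat scan and the missing end of collection remain.
- No safety endpoint is defined, this is a feasibility study, and many subjects will have short follow-up. **This stands in part.** It keeps the point modest, but asking at a visit that already takes place costs little.

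**Conclusion.** The point holds in a limited form. Active AE ascertainment is scheduled for the imaging visit only, while the scope in Section 8 has a start and no end. Later non-serious device-related or procedure-related events in evaluable subjects, including any after a repeat scan, depend on spontaneous reporting and are likely under-ascertained. Serious device effects are not affected in the same way.

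The size cannot be estimated from the documents. The up-to-135-day span is theirs; the event rates and capture fractions in the table are assumptions, and so is any delayed onset of skin effects. The zero-event bound of 2.7% to 3.0% shows what a clean result could claim for the imaging visit; it does not measure missed events.

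It would go too far to say that the study can describe only sensations during the scan, or that nobody would ask later. What can be said is that nobody is scheduled to ask. This does not touch the specificity endpoint. It is worth correcting because it improves the safety data at very small cost.

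**What to change.** 1. In Table 1 and Section 7.2.2, add an AE evaluation at the first biopsy visit: one eCRF question covering the time since the scan.
2. Add an AE evaluation at any repeat Imagio scan, and show that return in Table 1.
3. Where imaging and biopsy share a date, state how later events are captured, since a question asked that day adds almost no observation time.
4. Define procedure in Section 8 as scan, biopsy or both. If biopsy is included, also mark AE evaluation at the later biopsy and surgery visits that occur.
5. State an end of AE collection for all subjects. It should not stop at the biopsy itself: Table 1 can mark End of Study at that visit for concordant benign nodules, so ending there would narrow the present open-ended collection. It must also agree with the follow-up of enrollment failures in Section 7.5.
6. Reconcile the visit-limited sentence in Section 7.2.1 with Section 8.

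Cost: the core change adds one question at a visit that already takes place. The downside is slightly more data entry and a few more mild events to code. Item 3, and an end of collection after the last visit, also need the sponsor to say how subjects will be asked.

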7.2.2. Biopsy Procedure

Patients will be scheduled for initial biopsy within 45 days of the Imago OA/US procedure. Images of FNAB or Core Biopsy needle within the lesion are collected. If an FNAB is performed and results in insufficient cellularity for cytologic diagnosis and a repeat FNAB or core biopsy is required, this should be scheduled within 45 days after the first biopsy. The investigator is to ensure that the applicable site histopathology/cytology report is obtained. If a surgical procedure is applicable, it would be scheduled within 45 days after the second biopsy. Surgical and histology data will be collected.

7.3. Effectiveness Assessments

Primary Effectiveness Endpoint:

The primary metric for demonstration of feasibility is the incremental improvement in specificity. An improvement of approximately 5% would be indicative of a successful feasibility study.

Secondary Effectiveness Endpoints:

The percentage of correct downgrades is the next most important metric. Other metrics including sensitivity and negative likelihood ratios will be considered as supporting evidence.

7.4. Subject Withdrawal Criteria

Subjects may be discontinued from the study for the following reasons if deemed appropriate by the Sponsor and /or Investigator:

- Subject enters the study in violation of the protocol;
- Subject deviates from the protocol during the study;
- Pregnancy;
- Withdrawal of consent;
- If in the opinion of the investigator it is not in the subject's best interest to continue (reason for withdrawal must be specified); and,
- Termination of the study by the sponsor.

Protocol Deviations will be reviewed by the Sponsor on a routine basis and any deviation that results in the exclusion of the subject from the statistical analyses will be documented in the final clinical study report.

7.5. Enrollment Failures

Subjects deemed enrollment failures according to the quality assurance review or failure to complete the biopsy evaluations) will be replaced during the active enrollment period of the study. The following subjects will be considered enrollment failures and will be followed until all AEs are resolved:

- Subjects found to be ineligible after the scan is conducted;
- Subjects for whom the study device scans do not pass review (Seno Medical Director and/or Imaging Core Lab QAR review); and,
- Subjects who have incomplete or unusable biopsy results.

8. ADVERSE EVENTS, ADVERSE DEVICE EFFECTS, UNANTICIPATED ADVERSE DEVICE EFFECTS AND DEVICE DEFICIENCIES

For the purposes of this study, only Imago device-related adverse events (AE), unanticipated adverse device effects, procedure-related AEs and device deficiencies will be collected. AE and device deficiency collection will commence once the subject has provided written informed consent and the patient has entered OA Imago scanning room.

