3.2. Overall Study Design and Plan: Description

This is a feasibility study to assess Imago OA/US's ability to optimize the device algorithm specific to thyroid in order to detect the difference between benign and malignant thyroid nodules, and when appropriate, suspicious associated cervical lymph nodes. Imago evaluation will be performed according to the system's instructions for use. The study will initially consent subjects with at least one nodule classified as suspicious enough to warrant recommendation for biopsy according to CDU. In subjects with nodules very suspicious for malignancy in which there is a suspicion for metastatic lymph node disease that have also been recommended for biopsy, OA/US imaging will also be performed on the suspicious lymph node.

All selected subjects will undergo an Imago evaluation following consent and before any immediate fine needles aspiration biopsy (FNAB), core biopsy, or surgical excision. The decision whether to recommend and perform ultrasound guided FNAB or core needle biopsy will be based upon standard of care conventional diagnostic thyroid ultrasound findings. Imago IUS or OA findings will not be used as the reason to perform or to defer a biopsy or surgery.

A total of approximately 110 nodules classified as TI-RADS 1-5 scheduled for biopsy will prospectively screened (subject signed informed consent) to get 100 evaluable nodules (acceptable OA images (via Seno Medical Director and/or Independent Core Lab (ICL) quality assurance process) collected with acceptable cytology/histology final diagnosis data. It is expected that 10% of nodules will be enrollment failure leading to target evaluable analysis set of 100 nodules.

Enrollment failures in the study would consist of subjects who did not have acceptable OA images collected and/or valid cytopathology cell counts or histopathology considered adequate for diagnosis. (Cytopathology insufficiency rates vary from about 1.5% - 20%). Thyroid nodules that have undergone FNAB, but have insufficient cellularity for cytopathologic assessment, cannot be used unless repeat FNAB is performed and shows adequate cellularity for diagnosis).

The study will include a minimum number of thyroid nodules (TI-RADS 1-5) with adequate cytopathology or histopathology for diagnosis that include at least: 10 papillary thyroid carcinomas minimum, 10 Follicular neoplasms, and 30 benign nodules that include at least 5 Hashimoto (chronic lymphocytic thyroiditis) nodules.

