4. STUDY POPULATION

4.1. Number of Subjects

A total of approximately 110 subjects with 110 nodules classified as TI-RADS 1-5 scheduled for biopsy will prospectively screened (subject signed inform consent) to get 100 evaluable nodules (acceptable OA images (via

ICL QA process) collected with acceptable cytology/histology final diagnosis data). It is expected that 10% of nodules will be enrollment failure leading to target evaluable analysis set of 100 nodules.

Enrollment failures in the study would consist of subjects who did not have acceptable OA images collected and/or valid cytopathology cell counts or histopathology considered adequate for diagnosis. (Cytopathology insufficiency rates vary from about 1.5% - 20%. Thyroid nodules that have undergone FNA, but have insufficient cellularity for cytopathologic assessment, cannot be used unless repeat FNA is performed and shows adequate cellularity for diagnosis).

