9. IMAGING CORE LAB

To ensure consistency, the assessment of all imaging studies including **Imagio** will be managed by an independent Imaging Core Lab (ICL) to perform quality assurance review of collected images.

The Imaging Core Lab participating in this study will be:

Medical Metrics

[name]

[name]

[contact]

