12.5. Analyses

The following outlines the steps to be taken to develop and tune the image creation and colorization algorithm and to develop the guidelines and interpretations rules that will be subsequently applied by three independent readers. The steps will be performed collaboratively by the software engineer and Medical Director, with potential input at earlier stages from the site radiologists.

DEVELOPMENT OF GUIDELINES, INTERPRETATION RULES AND ESTIMATORS

1. Images and data will provide a basis for algorithm finalization, potential instrument improvements, the development of guidelines for interpretation of OA studies of thyroid nodules. Permit Imago OA optimizations with respect to specific parameters (e.g. illumination and detection conditions, laser pulse repetition rate, sound propagation characteristics, etc.). Optimizations may be different for thyroid nodules and for suspicious cervical lymph nodes.
2. Compare *in vivo* opto-acoustic images with those obtained from standard diagnostic thyroid ultrasound, color Doppler imaging (CDI), power Doppler imaging (PDI), strain elastography (SE), or shear wave elastography (SWE).

3. Compare the in vivo opto-acoustic features with those obtained from standard diagnostic thyroid ultrasound color Doppler imaging (CDI), power Doppler imaging (PDI), strain elastography (SE), or shear wave elastography (SWE).
4. Compare findings of conventional imaging modalities and those of opto-acoustic imaging with biopsy results for nodule size, location, type, and stage.
5. Develop Imago-based estimators for thyroid use.

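### The sponsor's Medical Director alone may fail a scan and so exclude a nodule, with no requirement to decide blind to pathology, whereas Section 4.1 leaves the decision to the core lab

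*Combined protocol and SAP*

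**What the plan says.** Two rules for who accepts an OA scan stand in the current text.

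- Section 4.1 defines evaluable nodules through the imaging core lab (ICL) only: "ICL QA process) collected with acceptable cytology/histology final diagnosis data".
- Section 3.2 defines the same nodules "via Seno Medical Director and/or Independent Core Lab (ICL) quality assurance process". Section 7.2.1 names the same two parties for repeat scans, and Section 7.5 lists as enrollment failures "Subjects for whom the study device scans do not pass review (Seno Medical Director and/or Imaging Core Lab QAR review").

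Section 7.5 says that enrollment failures "will be replaced during the active enrollment period of the study". Section 12.2 runs every analysis in one population, which requires OA data declared evaluable. It does not say who declares this, when, or with what knowledge.

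Section 12.5 describes development of the algorithm and interpretation rules, including a comparison of OA findings with biopsy results: "The steps will be performed collaboratively by the software engineer and Medical Director". Section 5.4 (Blinding) deals with subjects and site investigators and does not mention the Medical Director or the quality reviewers.

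**The concern.** The sections disagree on who decides. Under the wider rule, the person who may exclude a nodule also works on matching OA appearance to biopsy results. An OA picture that contradicts the biopsy is the one most likely to look like a poor image to someone who knows the answer. If such scans were failed, OA errors would leave the only analysis set and other nodules would take their place. Sensitivity, the negative likelihood ratio (NLR) and possibly the specificity gain would then favour the device. Section 1.4 says the results will shape the objectives and endpoints of the pivotal study, so an inflated estimate would carry forward.

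**Working it through.** **1. Who can fail a scan.** Section 4.1: core lab. Sections 3.2, 7.2.1 and 7.5: Medical Director and/or core lab. The *or* makes the Medical Director's judgement sufficient alone.

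**2. What failing does.** The subject is replaced (7.5) and the nodule leaves the single analysis population (12.2). No analysis brings failed scans back.

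**3. What the decider may know.** Step 4 of Section 12.5 uses biopsy results. Section 12.4 has clinical status summarised after 50 evaluable nodules, with enrollment still open. No section says that rule development waits until scan review is complete.

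**4. Timing.** Table 1, footnote 1 allows scan and biopsy on the same date. Section 7.2.1 allows a repeat scan only before biopsy. The pass/fail review has no deadline, so it may follow the biopsy; a failed scan then cannot be repeated.

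**5. The plan's own figure.** 100 evaluable nodules with 10% failures: 100 × 1.10 = 110, as stated (100/0.90 = 111.1, rounded up to 112, is the stricter form; the difference does not matter here). This implies about 110 − 100 = 10 failures of all kinds.

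**6. Sensitivity and NLR.** With D non-benign nodules, m missed by OA and k missed scans failed, sensitivity is (D − m)/(D − k). D = 20 is the plan's minimum of 10 papillary carcinomas plus 10 follicular neoplasms; m = 2 and k = 1 are assumptions.

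- All scans kept: 18/20 = 90.0%.
- One missed scan failed: 18/19 = 94.7%.
- NLR = (1 − sensitivity)/specificity. At fixed specificity it is multiplied by (1/19)/(2/20) = 0.526, a fall of about 47%.

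**7. Specificity gain.** Section 12.5 counts a benign nodule as correct at TI-RADS 1 or 2. With B benign nodules, g moved by OA into 1-2 and l moved out, the gain is (g − l)/B. The benign counts are assumed; about 80 would remain if 20 of 100 evaluable nodules are non-benign.

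- *Some moved out* (B = 82, g = 5, l = 2): 3/82 = 3.7%. Failing those two scans gives 5/80 = 6.3%, past the mark of approximately 5%.
- *None moved out* (B = 82, g = 3, l = 0): 3/82 = 3.66%. Failing two scans that OA left at 3-5 changes only the denominator: 3/80 = 3.75%. Reaching 5% would take 3/60, which is 22 failed scans.
- *Worst case, true gain zero*: failing k benign scans that were right on conventional ultrasound (CDU) and wrong on OA gives k/(B − k). For B = 33, 55, 88 and 99, the smallest k that passes 5% is 2 (2/31 = 6.5%), 3 (3/52 = 5.8%), 5 (5/83 = 6.0%) and 5 (5/94 = 5.3%).

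Replacement nodules are left out of steps 6 and 7.

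**The case against.** Much of the other side stands, and it limits what may be inferred.

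- **Two failed scans could carry the primary metric past 5%.** A reader might infer this generally. It needs benign nodules at baseline TI-RADS 1-2 that OA raised. TI-RADS 1-5 is eligible, so they can exist, but subjects must have a suspicious nodule scheduled for biopsy (4.2), and Section 12.4 may later restrict enrollment to categories 3-5. Few should be expected.
- **The Medical Director reviews scans knowing the pathology.** A reader might infer this too, but no section says so. Review is described with the imaging visit, Table 1 uploads images then, and biopsy may be up to 45 days later. Same-day biopsy is not same-day pathology. Access to biopsy results is stated for rule development; its overlap with scan review is inferred.
- **The final OA category usually does not exist at scan review.** Interpretation rules come first and the three independent readers follow. A reviewer could act only on an impression or on the site's own reading. The readers do not remove the problem, because they are analysed in the set left after exclusions.
- **The 10% allowance is not reserved for scan failures.** Section 12.4 assigns it to inadequate cytopathology; Sections 3.2 and 4.1 spread it over images and pathology.
- **Section 9 is not a contradiction.** It describes image assessment as "managed by an independent Imaging Core Lab (ICL) to perform quality assurance review of collected images", which is compatible with an added sponsor review. The conflict is between 4.1 and Sections 3.2, 7.2.1 and 7.5.
- **Criteria may exist elsewhere.** The revision history says imaging detail was moved to core lab documents that are not provided. They may hold criteria, timing and blinding, but they would not by themselves remove the authority the protocol gives the Medical Director.

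This is also a feasibility study with no formal test and only an indicative success mark.

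**Conclusion.** The point holds as a gap that permits outcome-dependent exclusion, not as evidence that it will occur. The protocol gives two rules for who accepts a scan. The wider one lets a person involved in developing the OA rules remove a nodule from the only analysis set, without any stated blinding or deadline. Feasibility status lowers the stakes but does not excuse the gap.

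The clearest consequence is for sensitivity and NLR, which are supporting measures: one selectively failed scan among 20 non-benign nodules is worth about 5 percentage points of sensitivity. For the primary specificity gain the effect is material only where OA raised benign nodules from TI-RADS 1-2, and negligible otherwise. All these sizes rest on assumed counts. The change should be made; the sample size of 110 is unaffected.

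**What to change.** Reconcile Sections 3.2, 7.2.1 and 7.5 with Section 4.1:

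- The core lab quality reviewer alone makes the final pass/fail decision, from the images only, on written technical criteria and without the pathology result.
- The decision is date-stamped before that nodule's pathology is released to those deciding.
- The Medical Director may still ask for a repeat scan before biopsy, but may not fail a scan for replacement.
- Each failed scan is logged with its date and reason.
- Section 12.2 refers to this decision as the meaning of OA data declared evaluable.

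The cost is protocol wording, a line in the core lab manual and a simple control on pathology access, needed because sponsor monitors verify case report data against medical records (Section 10). No new reader is needed, since Table 1 already schedules upload to the core lab and Section 9 already gives it quality review. Section 13.6 sends images to the sponsor and/or the core lab as applicable, so it should state that every study scan goes to the core lab. The downside is that some scans the Medical Director would reject stay in.
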